8.3 Protein Multiplex Arrays (Plasma)

Peripheral blood will be collected for plasma from each subject at the following timepoints: baseline, end of monotherapy lead-in on Day 8 (biomarker cycle of dose expansion cohort only), end of first cycle of combination therapy on Day 29 (biomarker cycle of dose expansion cohort only), every restaging, disease progression or treatment discontinuation, off treatment follow-up, and for complete responders on long term follow-up. Refer to *Study Manual* for collection, processing, and submission details.

Plasma will be stored by the Duke Phase I Biomarker Laboratory under the direction of [name]. Markers of inflammation will be analyzed in the Duke Phase I Biomarker lab. Analyses will be performed on pre-treatment and on-treatment samples. Analyte levels, and changes in analyte levels, will be correlated with clinical outcome (PFS, OS). Plasma and serum samples will be evaluated by ELISA for protein markers that may be associated with sensitivity or resistance to pembrolizumab. These may include CRP and other markers of inflammation, including but not limited to IFNy, IL1 β , IL4, IL6, IL7, IL10, IL12, IL17A, IL17E, and IL23.

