9.1.3 Exploratory Endpoints

CD8 and PDL1 staining measured by IHC are the primary biomarker endpoints for this study. Descriptive statistics will be provided for each of these endpoints at each time point (pre-, P, and on-treatment, OT) and for the change P vs OT.

For continuous CD8 and PDL1 expression measures (e.g., percentages), the paired t-test will be used to compare change in P vs OT. We expect approximately 25 patients to have paired measurements. With 25 patients studied a difference of 0.53 standard deviation (SD) can be detected with 90% power (1-sided $\alpha=0.1$). With this sample size differences of 13%, 27%, and 40% can be detected with 80% power assuming SDs of 0.25, 0.5, and 0.75, respectively.

For dichotomous paired proportions (e.g., <2+ versus >2+ by IHC) McNemar's test will be used to test the null hypothesis that the difference in P and OT proportions is 0 versus the alternative that it is > 0 or < 0. With 25 paired patient samples studied 79% power is achieved to detect the difference illustrated in Table 1a below and 86% power is achieved to detect the difference illustrated in Table 1b (2-sided $\alpha=0.1$).

Table 1a: Alternative hypothesis resulting in 79% power using McNemar's test (2-sided $\alpha=0.1$).

	Post Treatment		Total
Pre Treatment	<2+	>2+	
<2+	0.15	0.45	0.60
>2+	0.10	0.30	0.40
Total	0.25	0.75	1.00

Table 1b. Alternative hypothesis resulting in 86% power using McNemar's test (2-sided $\alpha=0.1$).

	Post Treatment		Total
Pre Treatment	<2+	>2+	
<2+	0.10	0.50	0.60
>2+	0.10	0.30	0.40
Total	0.20	0.80	1.00

Similar analyses will be conducted for other biomarkers as described in Section 8.0. No adjustments will be made for multiple comparisons. Data transformations or non-parametric methods will be used as appropriate.

Associations between changes in immune infiltrates and outcomes (PFS, RR, OS) will be explored using Cox regression (PFS), 2-sample t-tests or non-parametric Wilcoxon rank-sum tests, or the Chi-square test (6-month PFS, RR) based on the distribution and structure of the data (i.e., either parametric or non-parametric methods will be used as appropriate).

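### Section 9.1.3 relates biomarker change to outcome without the pre-treatment level, so a prognostic baseline can appear as an effect of change; a baseline-plus-change model should be reported beside it

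*Combined protocol and SAP*

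**What the plan says.** Section 9.1.3 sets the analysis in one sentence: "Associations between changes in immune infiltrates and outcomes (PFS, RR, OS) will be explored using Cox regression (PFS), 2-sample t-tests", or Wilcoxon rank-sum tests, "or the Chi-square test (6-month PFS, RR) based on the distribution and structure of the data". Cox regression is tied to PFS and chi-square to 6-month PFS and RR; no method is tied expressly to OS. No covariates are listed.

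The same section expects about 25 patients with pre-treatment (P) and on-treatment (OT) readings. It extends the approach to other markers: "Similar analyses will be conducted for other biomarkers as described in Section 8.0". For plasma, Section 8.3 states: "Analyte levels, and changes in analyte levels, will be correlated with clinical outcome (PFS, OS". The synopsis, under Correlative Studies, also plans to explore biomarker expression against outcome. No section puts the pre-treatment level and the change into one model.

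The protocol's background treats these markers as possibly prognostic. Section 1.2.1.1 says that CD8+ T-cell presence seems to go with better prognosis in many solid tumors. Section 1.1 links high PD-L1 expression to worse prognosis.

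**The concern.** Change is OT minus P, so a patient who starts high tends to show a smaller rise. If the starting level is itself related to PFS, a change-only analysis shows an association even when the change has no effect. The sign is opposite to that of the baseline effect: if high baseline CD8 is favourable, a CD8 rise on pembrolizumab is pushed towards looking harmful. If the on-treatment level is what matters, its effect is diluted.

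Section 1.3 makes mechanisms of sensitivity and resistance an overall goal, and exploratory objective 2 links biomarker changes to outcome. Section 9.1.3 makes no multiplicity adjustment, so a systematic false lead would be hard to tell from a real one.

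**Working it through.** **Plan figures.** The plan gives no power or error figure for the change-versus-outcome analyses. Its paired-comparison figures at n = 25 do reproduce: 0.53 SD at one-sided 0.1 gives 90.7% (stated 90%), and the McNemar alternatives in Tables 1a and 1b give 79.1% and 86.3% (stated 79% and 86%).

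**Slope on change alone.** Let D = OT − P, SD(P) = 1, SD(OT) = r and corr(P, OT) = ρ. Then cov(P, D) = ρr − 1, cov(OT, D) = r² − ρr and var(D) = 1 + r² − 2ρr. For small effects:

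- only P matters, effect b: slope on D = b(ρr − 1)/var(D)
- only OT matters, effect b: slope on D = b(r² − ρr)/var(D)

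With r = 1 these are −(1 − ρ)/[2(1 − ρ)] = −0.5 and +0.5 times b, at any ρ below 1. With ρ = 0.5:

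| OT/P SD ratio | only P matters | only OT matters |
|---|---|---|
| 0.75 | −0.77b | +0.23b |
| 1 | −0.50b | +0.50b |
| 1.25 | −0.29b | +0.71b |
| 1.5 | −0.14b | +0.86b |
| 2 | 0 | +1.00b |

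**The plan's own tables.** Tables 1a and 1b hold the only joint P/OT distributions in the documents. They are planning alternatives for a dichotomised marker, not data.

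- 1a: var(P) = 0.40 × 0.60 = 0.24; var(OT) = 0.75 × 0.25 = 0.1875; cov = 0.30 − 0.40 × 0.75 = 0; var(D) = 0.4275. Slopes: −0.24/0.4275 = −0.56 and 0.1875/0.4275 = +0.44.
- 1b: var(OT) = 0.80 × 0.20 = 0.16; cov = 0.30 − 0.40 × 0.80 = −0.02; var(D) = 0.24 + 0.16 + 0.04 = 0.44. Slopes: −0.26/0.44 = −0.59 and 0.18/0.44 = +0.41.

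In both tables only patients who start low can rise, so no riser is high at baseline. Among non-risers, 0.40/0.55 = 73% (1a) and 0.40/0.50 = 80% (1b) are. A chi-square test of rise against response would largely compare low starters with high starters.

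**Cox simulation.** Assumed: 25 pairs, normal markers, equal SDs, exponential times, no censoring, Wald test at two-sided 0.10, 1,500 runs per setting. With no effect at all, both models reject in 10% to 13%.

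| Rejections for change | ρ = 0 | 0.3 | 0.5 | 0.7 |
|---|---|---|---|---|
| Only P matters, HR 0.67 per SD, change-only | 35% | 27% | 21% | 18% |
| Only P matters, HR 0.5 per SD, change-only | 59% | 45% | 36% | 29% |
| Only OT matters, HR 0.5 per SD, change-only | 61% | 47% | 37% | 24% |
| Only OT matters, HR 0.5 per SD, with P in model | 88% | 86% | 79% | 68% |

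In the baseline-only settings, adding P brings rejection to 10% to 14%. For an OT log hazard ratio of −0.693, the change-only median estimate is −0.28 to −0.32 (41% to 46% of the truth); with P in the model it is −0.72 to −0.74. At ρ = 0.5, the 36% false-positive rate becomes 57% at SD ratio 0.75, 14% at 1.5 and 11% at 2.

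**t-test form.** Halving is a regression result. With equal SDs, an OT-only group difference shrinks to (1 − ρ) in raw units and to √[(1 − ρ)/2] when standardised: 0.71, 0.59, 0.50 and 0.39 at ρ = 0, 0.3, 0.5 and 0.7. A baseline-only odds ratio of 2 per SD gives 28%, 23%, 20% and 16% false positives.

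**Where the adjusted model does worse.** These runs also had 25 pairs and two-sided 0.10, with ρ = 0.3 to 0.7.

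- Change itself drives outcome, HR 0.5 per SD of change: power is 89% to 93% change-only and 74% to 86% with P added. At HR 0.7 it is 48% to 49% against 38% to 43%.
- P and OT are equally noisy readings of a stable prognostic level T. Then D is the difference of two errors, so cov(T, D) = 0 and change-only is unbiased. The best predictor of T weights both readings equally, and w(P + OT) = 2wP + wD, so the adjusted change coefficient picks up T. At HR 0.5 per SD of T, false positives are 10% to 12% change-only and 28% to 33% adjusted.

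**The case against.** The strongest objection is that adjustment is not neutral. CD8 and PDL1 come from small biopsies about a week apart (Section 8.1), so sampling error is plausible, and under a stable, noisily measured level it is the adjusted model that misleads. If the change itself matters, change-only is the correct model and adjustment costs power. In the OT-only case the adjusted change coefficient is algebraically the OT coefficient given P, so the power gain concerns a different quantity. All of this stands, and it rules out making the adjusted coefficient the sole result.

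The size also rests on similar SDs at the two times. The documents give none, so halving is a conditional statement.

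On scope, the sentence in 9.1.3 concerns immune infiltrates, which covers CD8; PDL1 comes in only on a broad reading or through the extension to other markers. The Cox covariates are unstated, so a reader who infers that baseline is excluded goes beyond the text. Section 8.3 and the synopsis relate levels as well as changes to outcome, so a prognostic baseline may be noticed. But separate analyses of level and change do not show whether the change association survives once the level is held fixed.

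Finally, these analyses are exploratory, with no decision rule attached. That limits the weight of the point but does not remove it.

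**Conclusion.** The point holds as a low-cost improvement to an exploratory analysis; the primary PFS result is untouched. As written, 9.1.3 cannot tell a baseline effect from a change effect within one analysis. Where the pre-treatment level is prognostic and P and OT have similar SDs, the change-only coefficient carries about minus half of the baseline effect, and an on-treatment effect is about halved. The distortion is larger when OT varies less than P, smaller when it varies more, and absent at SD ratio 2 with correlation 0.5. It is also absent if outcome depends on the change itself. The hazard ratios, correlations, SD ratios and normality used here are assumptions.

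A reader might infer that the planned analysis will yield false change effects and that the adjusted coefficient should replace it. The documents do not support that: they give no SDs for P and OT, no correlation beyond the two planning tables, no size for measurement error, and nothing to show whether level or change drives outcome.

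**What to change.** In Section 9.1.3, and for the plasma changes in Section 8.3, add wording such as: *For PFS and OS, Cox models containing the pre-treatment level and the change together will be reported beside the change-only result. A change-only association will not be read as an effect of change unless it persists with the pre-treatment level in the model. For RR, a logistic model with the same two covariates is supportive only.* The logistic model is limited because, with about 25 patients, the rarer response class has at most 12.

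State the limits in the same place: adjustment loses some power if change alone drives outcome, and with measurement error in the pre-treatment reading the adjusted change coefficient can pick up the underlying level. Neither result should be taken alone as definitive.

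The cost is a few sentences and no new data, since every patient with a change already has a pre-treatment value. The Cox models would rest on about 23 PFS events (25 × 32/35, from the plan's expected 32 events in 35 patients), which is thin but workable for two covariates in an exploratory analysis.

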10.0 SAFETY

Refer to *Study Manual* for required reporting forms.

10.1 Adverse Events

An adverse event (AE) is defined as any untoward medical occurrence in a patient or clinical investigation subject administered a pharmaceutical product and which does not necessarily have to have a causal relationship with this treatment. An adverse event can therefore be any unfavorable and unintended sign (including an abnormal laboratory finding, for example), symptom, or disease

temporally associated with the use of a medicinal product or protocol-specified procedure, whether or not considered related to the medicinal product or protocol-specified procedure. Any worsening (i.e., any clinically significant adverse change in frequency and/or intensity) of a preexisting condition that is temporally associated with the use of the supporting company product(s), is also an AE.

Changes resulting from normal growth and development that do not vary significantly in frequency or severity from expected levels are not to be considered AEs. Examples of this may include, but are not limited to, teething, typical crying in infants and children and onset of menses or menopause occurring at a physiologically appropriate time.

Supporting company product includes any pharmaceutical product, biological product, device, diagnostic agent or protocol-specified procedure, whether investigational (including placebo or active comparator medication) or marketed, manufactured by, licensed by, provided by or distributed by the supporting company for human use.

AEs may occur during the course of the use of supporting company product(s) in clinical trials or within the follow-up period specified by the protocol, or prescribed in clinical practice, from overdose (whether accidental or intentional), from abuse and from withdrawal.

Progression of the cancer under study is not considered an AE unless it is considered to be drug related by the Investigator.

AEs will be documented from the date of first dose of study drug through 30 days after the last dose of study drug. All Grade 2-5 AEs as well as special reporting circumstances, such as exposure via a parent during pregnancy or breast-feeding, overdose, medication error, misuse, abuse, off-label use or occupational exposure must be recorded on the CRF.

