5.1 Screening Period

During the Screening Period, subjects are consented and screened for the study. Informed consent must be obtained before initiation of any screening procedure that is performed solely for the purpose of determining eligibility for this study. Evaluations performed as part of routine care before informed consent can be considered as screening evaluations if done within the defined screening period, and if permitted by the local Institutional Review Board (IRB)/ Independent Ethics Committee (IEC) policies. Study eligibility is based on meeting all of the inclusion criteria and none of the exclusion criteria (refer to [Section 4.0](#)) before the first dose of study drug on Cycle 1 Day 1.

The following study procedures must be done within 28 days prior to Cycle 1 Day 1:

- Demographics
- Medical and cancer history
- Physical examination
- Height
- Vital signs and weight
- Concomitant medications
- ECOG performance status (perform or repeat within 7 days prior to dosing on Cycle 1 Day 1)
- Thyroid function tests
- Adverse event assessment (review of baseline symptoms)
- Tumor assessment (CT and/or MRI scans)
- Blood tumor marker, if clinically indicated (e.g., CEA or CA19-9)
- Archived tumor tissue (if available)
- PBMC (may be collected pre-dose on Cycle 1 Day 1)
- Plasma (may be collected pre-dose on Cycle 1 Day 1)
- Whole blood (may be collected pre-dose on Cycle 1 Day 1)

The following study procedures must be done within 7 days prior to Cycle 1 Day 1:

- CBC with differential
- Chemistries including liver function tests (LFTs)
- Serum pregnancy test (only for women of childbearing potential)

- Tumor biopsy (only applicable to patients in dose expansion that have lesions amenable to safe biopsy)

Subject eligibility is determined using lab results obtained up to 7 days prior to Cycle 1 Day 1. Any laboratory assessments repeated on Cycle 1 Day 1 must meet eligibility requirements. The Screening Period ends upon receipt of the first dose of study drug or final determination that the subject is ineligible for the study.

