8.1 Tumor Tissue Biomarkers

Archived formalin fixed paraffin embedded (FFPE) tumor tissue will be collected for all subjects (if available). Refer to *Study Manual* for collection, processing, and submission details.

For patients accrued to the dose expansion cohort, pre-treatment and on-treatment tumor biopsies will be performed only on patients who have a tumor lesion that is amenable to safe biopsy. In the biomarker cycle, patients will undergo tumor biopsy up to 1 week before starting treatment (i.e., pre-treatment) and will undergo a second tumor biopsy on Day 7 or 8 prior to start of oxaliplatin and capecitabine (i.e., on-treatment). The preferred type of biopsy is a core biopsy: five 18-gauge core needle biopsies (diameter about 2 mm) with a throw length of approximately 2 cm will provide adequate tissue for study. Refer to *Study Manual* for collection, processing, and submission details. Note: Those patients accrued to the dose expansion cohort who do not have a tumor lesion that is amenable to safe biopsy will only have blood-based biomarker collections in the biomarker cycle (ie. Cycle 1).

We will interrogate these tissue specimens using whole exomic sequencing studies, spatial transcriptomic analysis, and proximity ligation assays to spatially resolve the impact of pembrolizumab on tumor T cell/PMN-MDSC infiltration and NLRP3 inflammasome activation. These data will be correlated with mutations associated with this resistance pathway as well as with clinical response. This work will leverage a rare tissue bank of pre- and post-pembro tumor specimens to reveal a series of novel pharmacologic targets and potential biomarkers capable of overcoming immunotherapy resistance and improving the management of patients with gastrointestinal malignancies.

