10.2 Serious Adverse Events

A serious adverse event (SAE) is defined as any untoward medical occurrence that at any dose:

1. Results in death.
2. Is immediately life-threatening (ie, in the opinion of the Investigator, the AE places the subject at immediate risk of death; it does not include a reaction that, had it occurred in a more severe form, might have caused death).
3. Requires inpatient hospitalization or results in prolongation of an existing hospitalization.
4. Results in persistent or significant disability or incapacity. (Note: The term "disability" refers to events that result in a substantial disruption of a subject's ability to conduct normal life function.)
5. Is a congenital anomaly or birth defect.
6. Is an important medical event (Note: The term "important medical event" refers to an event that, based upon appropriate medical judgment, may not be immediately life-threatening or result in death or hospitalization, but may jeopardize the subject or require intervention to prevent one of the other serious outcomes listed under the definition of SAE. Examples of important medical events include intensive treatment in an emergency room or at home for allergic bronchospasm; blood dyscrasias, or convulsions that do not result in hospitalization; or development of product dependency or product abuse.)

SAEs and/or follow up to SAEs including death due to any cause other than progression of the cancer under study, that occurs from the date of the first dose of study drug through 30 days following the last

dose of study drug, whether or not related to study drug(s), must be recorded on the CRF and must be reported within 2 business days supporting companies. External sites should report SAEs to the Duke study team within 24 hours. Reporting instructions for external sites can be found in the REDCap study eManual.

All SAEs must be followed until resolution, return to baseline condition, or stabilization. Any SAEs that are ongoing at the time the clinical database is closed will be reported to supporting companies as unresolved.

The initial report for each SAE or death should include at minimum the following information:

- protocol number and title
- patient initials, study identification number, sex, age
- date the event occurred
- description of the event
- seriousness criteria
- event causality or causal relationship
- study drug name(s)
- dose level and cycle number at the time the event occurred
- description of the patient's condition

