10.3 Events of Clinical Interest

Select (non-serious and serious) adverse events called Events of Clinical Interest (ECI) that occur from the date of the first dose of study drug through 30 days following the last dose of study drug, must be recorded on the CRF and must be reported within 2 working days to Merck Global Safety.

An ECI for this study is any hepatic toxicity that is \geq Grade 2 or any grade resulting in dose modification or use of systemic steroids to the adverse event. Such adverse events include but are not limited to; hepatitis, autoimmune hepatitis, and transaminase elevations (ALT and/or AST).

Any overdose of pembrolizumab (1,000 mg or greater) is also considered an ECI for this study and should be reported as such, regardless of the outcome.

ECI Reporting Procedure:

Immediately upon awareness of an ECI, the Investigator (or designee) completes the **DCI SAE Report Form** and will submit the form within 2 business days of knowledge of the event to the funding company. External sites should submit the form within 24 hours to the Duke study team via the REDCap SAE reporting tool.

Note: It is imperative that initial ECI reports are submitted as soon as possible (within 2 business days of knowledge of the event) with available information to the supporting company. Missing and/or clarified event information may be provided in a follow-up report.

Follow-up information including severity, action taken, concomitant medications, and outcome should be communicated to the funding company as soon as possible using the same form mentioned above.

The Lead PI will review the report form with accompanying source document, sign page 5, and the PI or designee will then promptly submit it to the funding company.

Within two business days of receipt, the study team will also submit the SAE report form and other relevant safety information to the following supporting company:

Merck Global Safety
ATTN: Worldwide Product Safety
[contact]

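### Mandatory AE and SAE capture in Section 10 starts at first dose, so a complication of the expansion cohort's pre-treatment research biopsy that occurs before dosing need not be recorded as an AE or reported as an SAE

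*Combined protocol and SAP*

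**What the plan says.** Three windows in Section 10 open on the same day.

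- AEs (Section 10.1): "AEs will be documented from the date of first dose of study drug through 30 days after the last dose of study drug".
- SAEs (Section 10.2): the duty to record on the CRF and report covers an event "that occurs from the date of the first dose of study drug through 30 days following the last" dose.
- Events of clinical interest (Section 10.3): those that "occur from the date of the first dose of study drug through 30 days following the last dose of study drug".

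Section 10.1 also defines an AE to include a sign, symptom or disease "temporally associated with the use of a medicinal product or protocol-specified procedure".

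For the expansion cohort, Section 8.1 says that "patients will undergo tumor biopsy up to 1 week before starting treatment (i.e., pre-treatment"), and that a second biopsy follows on Day 7 or 8, before chemotherapy starts. The preferred sample is five cores with an 18-gauge needle. Section 5.1 lists the first biopsy among the procedures for the 7 days before Cycle 1 Day 1. Only patients with a lesion that can be biopsied safely have it.

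Other sections also deal with AE capture. Section 5.1 includes a screening item, "Adverse event assessment (review of baseline symptoms"). Sections 5.5 and 7.0 say that AEs are documented or monitored for the whole study and give no start date. Appendix D marks AE assessment in the screening column and adds a footnote to record events as they occur during the study. Section 10.2 separately sends SAEs to the local IRB under institutional guidelines, and any study-related death to the IRB within 24 hours.

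**The concern.** The first biopsy is invasive and, as far as the documents show, is done for research. It supplies the CD8 and PDL1 comparison in Section 9.1.3 and is not among the inclusion criteria in Section 4.1. Harm from a research procedure is something that a trial's safety system would be expected to pick up. Here the stated start of capture falls after the procedure.

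The gap is also selective, because a serious complication is the kind most likely to prevent dosing. Laboratory values repeated on Cycle 1 Day 1 must still meet eligibility (Section 5.1), including hemoglobin of at least 9 g/dL (Section 4.1), so a large bleed could disqualify a patient. Section 4.2 excludes major surgery within 28 days and, with one exception, infection needing systemic treatment within 2 weeks before the start of study drug. For a patient lost in this way the Section 10 window never opens.

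At stake is whether the coordinating center is told promptly of a biopsy harm while other patients are being scheduled for the same procedure.

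**Working it through.** No power or sample-size figure is involved. The check sets the dates and duties side by side.

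**Length of the gap.** The biopsy is taken up to 7 days before first dose and capture starts on the day of first dose, so the uncovered interval is up to 7 days. The second biopsy, on Day 7 or 8, comes after first dose and is inside the window.

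**The same complication in three patients.**

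| Patient | AE record required by 10.1? | SAE report required by 10.2? | What else applies |
|---|---|---|---|
| A: event after the first biopsy, resolved before dosing, then dosed | No | No | Could be noted as a baseline symptom (5.1) |
| B: event after the first biopsy, never dosed | No, the window never opens | No | Not evaluable for toxicity, since Section 3.1 requires study treatment |
| C: event after the Day 7 or 8 biopsy | Yes, if Grade 2 to 5 for CRF entry | Yes, if serious | Full Section 10 procedure |

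The same procedure with the same complication is handled differently in A and B than in C.

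**Do the other routes close the gap?**

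1. The Section 5.1 screening review can put the event on file as a baseline symptom. Nothing there labels it procedure-related or triggers an SAE report.
2. Sections 5.5 and 7.0 give no start date, and 5.5 refers to 10.1 and 10.2 for definitions and SAE reporting. If their wording is meant to include screening, it is inconsistent with the first-dose start in Section 10.
3. Appendix D has a mark at screening. In the extracted table the whole-study span follows that mark, so it is unclear whether the footnote reaches back to screening. If it does, the same inconsistency arises.
4. The IRB sentences depend on institutional rules or on a death. They require neither CRF entry nor the 24-hour report from an external site to the coordinating center.

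Section 6.5.1 records concomitant medication from signed consent. A drug given for a pre-dose complication therefore has to be on the CRF, while Section 10 does not require the complication itself to be there.

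**How many biopsies.** Section 9.1.3 expects about 25 patients with paired samples. Each had one pre-treatment biopsy, so 25 × 1 = 25 fall before the window, out of 25 × 2 = 50 biopsies in those patients, or one half. This is a lower figure: patients with only the first biopsy add to it. The expansion cohort has 30 evaluable patients, all dosed by the Section 3.1 definition. The number biopsied but never dosed is not given.

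**How many events.** The documents give no biopsy complication rate, so no expected count of missed events can be derived.

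**The case against.** A reader might infer that pre-dose biopsy complications are never recorded or reported. The documents do not support that. Sections 5.1, 5.5 and 7.0 and Appendix D each give a route by which such an event could be written down, and the IRB sentences in Section 10.2 state no first-dose limit. Section 11.7 has the Lead PI monitor and tabulate AEs continuously, again without a start date, so it cannot be said that the Lead PI would be unable to see a biopsy harm. The Safety Oversight Committee reviews annually, so a window opened a week earlier would not by itself give it earlier sight of an event.

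Four further points count against a strong claim.

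- The AE definition opens with "any untoward medical occurrence in a patient or clinical investigation subject administered a pharmaceutical product", and the SAE definition is also framed in terms of dose. Whether either reaches a patient not yet dosed is arguable.
- The roughly 25 paired patients were all dosed, so they do not include patient B. A complication that starts or worsens after first dose can still fall inside the window.
- The safety objective concerns the drug regimen. Restricting toxicity evaluability to treated patients suits that objective, and no estimate of biopsy risk is planned that could be biased.
- The Study Manual, the eManual and the external site monitoring addendum are not among the documents and may deal with procedure events.

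These points limit the finding but do not remove it. None of the routes in the protocol requires a pre-dose biopsy complication to be recorded as a procedure-related AE or reported as an SAE to the coordinating center. The doubt over the definition is itself a reason to state the rule.

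**Conclusion.** The point holds in a limited form. Section 10 sets an explicit start date that falls after a research biopsy, so the gap comes from a stated rule and not from a missing detail. A complication of that biopsy before dosing is outside mandatory AE recording and SAE reporting, and a biopsied patient who is never dosed is outside it altogether. The whole-study wording in Sections 5.5 and 7.0 and Appendix D is inconsistent with Section 10 and should be reconciled with it.

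The size is up to 7 days for at least about 25 biopsies. How many events this would miss is unknown; any probability would rest entirely on an assumed complication rate. Neither the efficacy analyses nor the planned safety description of the regimen is shown to be affected. The conclusion assumes that the biopsy is done for research, which is inferred from Sections 4.1 and 9.1.3, and that no manual outside the documents already covers the interval.

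**What to change.** In Sections 10.1 and 10.2, start capture of SAEs, and of AEs related to a protocol-specified procedure, at the first such procedure or at signed consent. Keep first dose as the start for all other AEs. State in the AE definition that the procedure limb applies before dosing.

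Align Sections 5.5 and 7.0 and Appendix D with the new start dates.

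List procedure-related events separately for consented patients who were biopsied but never dosed. The listing should be based on consent, not accrual: under Section 3.1 a patient made ineligible by a complication may count as a screen failure and would drop out of a listing of accrued patients.

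The cost is an amendment to the wording, a few more reports in the pre-dose week, and what should be a small CRF change, although the CRF is not among the documents. No procedure is added and the efficacy analyses stay as they are.
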